6. SAFETY

6.1. Primary Safety (Bleeding) Endpoint

The primary safety endpoint is any bleeding event

6.1.1. Definition

Any bleeding event is defined as the composite of major, CRNM, and minimal bleeding events

- Any bleeding = Major + CRNM + Minimal

The primary window for analysis of any bleeding event is the up to Day 10-14 visit observation period.

The following maps the location in eCRF of the investigator reported components needed in the definition of any bleeding:

Any bleeding	eCRF Page # (s)	Comments
Bleeding Category	Bleeding Event	Classify the bleeding category as defined in Attachment 2 of the protocol: 
 • Major Bleeding in Surgical Setting • Clinically Relevant Nonmajor Bleeding • Minimal Bleeding

6.1.2. Safety (Bleeding) Analysis Methods

a) In support of the dose escalation decision within Part 1, the following will be summarized.

- The number of subjects with Major bleeding up to Day 10-14 visit observation period and the corresponding lower bound of 1-sided 90% confidence interval for dose escalation by cohort/dose. If the computed lower bound based on the observed rates, in the highest JNJ-64179375 dose studied, is greater than a predefined threshold, e.g., 2%, 3% or 4%, then it could signal that further dose escalation be prohibited.

The lower bound of 1-sided 90% confidence interval used for comparison to the threshold is a one sample CI, which is equivalent to a lower bound of 2-sided 80% CI, that can be obtained using the Exact method in PROC FREQ (in SAS).

- The number of subjects with Any bleeding up to Day 10-14 visit observation period and the corresponding lower bound of 1-sided 90% confidence interval for the between JNJ-64179375 dose and apixaban (or cumulative apixaban beginning from cohort 1) treatment difference of event rate for dose escalation using greater than zero threshold by cohort/dose.

The lower bound of 1-sided 90% confidence interval used for comparison to the threshold (0) is a two sample CI will be based on Miettinen and Nurminen (1985) method and will be computed in SAS following the closed form formulas for the method (Garner W). This method, unlike the most widely known Wald method (ie, normal approximation), does not produce undesirable results in extreme cases (eg, when the proportions are near 0 or 1).

Summaries from the above, will be presented as side by side for CEC adjudicated, investigator reported and best available, where best available is always CEC adjudicated if a subject has both CEC adjudicated and investigator reported events.

- Continual Reassessment Method (CRM), a model based approach commonly used in oncology dose escalation study to determine MTD, will also be employed to predict event rates in next higher dose to guide the dose escalation process.
- b) For the unblinded data review planned after all subjects are expected to have completed the Day 10-14 visit for Part 1, the following summary and analysis will be performed.
- Incidence of Any bleeding with associated component events will be summarized by treatment group for the safety analysis set. 90% confidence intervals for the odd ratio of each JNJ-64179375 dose, as well as combined JNJ-64179375 doses, over apixaban event rate with respect to Any bleeding and its associated component events will also be constructed.
- Dose response of JNJ-64179375 with respect to Any bleeding will be assessed using a two-stage generalized least squares approach model fitting methodology (Pinheiro et al, Stat in Med, 2013). That is, in the first stage, ANOVA-type model to the binary, Any bleeding data, based on the logistic regression model are fit using dose as factor. In the second stage, various candidate models (on logit scale) are fit using the estimates (from first stage) employing the multiple comparison and modeling (MCP-Mod) approach to the dose levels and associated variance-covariance matrix estimates from stage 1. The following candidate models will be considered: linear, emax, exponential, logistic and sigEmax. Dose-response effect are tested using a model-based multiple contrast test to select one (or several) model(s) from the significant shapes. The best fitting model to the data are picked using either the gAIC or aveAIC model selection criterion. The model

with the smallest gAIC or aveAIC value is considered to fit the data best. Plots of the observed data and model fit including the 95% confidence intervals of the fitted lines will be presented using response rate on the y-axis and dose on the x-axis.

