evaluable and the true underlying total VTE event rates are 15%, 10%, 8%, and 6% at potential doses of JNJ-64179375 of 0.3, 0.6, 0.9, and 1.2 mg/kg, respectively, with a total sample size of 1,200 subjects, the study is expected to have over 90% power to declare proof-of-efficacy, which is defined as either a statistically significant dose-response trend or a total VTE event rate lower than 30% in the pooled doses of JNJ-64179375 at a 1-sided, 2.5% α -level. The exact power will vary because of the nature of the adaptive study design.

For comparison with apixaban in Part 2, if the true underlying total VTE and any bleeding event rates are as specified in Table 7, a simulation study demonstrates that there will be approximately 90% probability to identify a dose within the dose range of 0.3 to 1.2 mg/kg, of which both the model-predicted total VTE and any bleeding event rates met the prespecified noninferiority (NI) criterion (the upper bound of the 1-sided 90% CI for the odds ratio [JNJ-64179375 to apixaban] is equal to or lower than 1.5 for total VTE and any bleeding events).

Table 7:Assumed Efficacy and Safety Event Rates by Treatment Group in Sample Size Determination
for Part 2

	JNJ-64179375				Apixaban
	0.3 mg/kg	0.6 mg/kg	0.9 mg/kg	1.2 mg/kg	2.5 mg bid
Total VTE					
(Efficacy)	15%	10%	8%	6%	15%
Any Bleeding					
(Safety)	5%	6%	7%	8%	8%

bid=twice daily; VTE=venous thromboembolism

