Following primary unilateral elective TKR surgery, eligible subjects in Part 1 will be randomly assigned to a single-ascending IV dose of JNJ-64179375 or apixaban 2.5 mg given orally twice daily for 10 to 14 days. Six cohorts of up to approximately 50 unique subjects per cohort (total of up to approximately 300 unique subjects) are planned but the number of cohorts and the size of each cohort may be adjusted based on the ongoing unblinded data review by the Operations Committee (OC). Within each cohort, subjects will be randomized in a 4:1 ratio to JNJ-64179375 or apixaban, respectively (ie, approximately 40 subjects to JNJ-64179375: approximately 10 subjects to apixaban). JNJ-64179375 will be administered in a dose-escalation manner, with planned doses of 0.3, 0.6, and 1.2 mg/kg in Cohorts 1, 2, and 3, respectively. In Part 1, the OC will be responsible for reviewing ongoing safety and efficacy data by unblinded subject treatment assignments approximately every 1 to 3 weeks. Subjects enrolled in the optional cohorts will receive doses of JNJ-64179375 in the range of 0.1 to 1.8 mg/kg, which will be dependent on the available preliminary safety, tolerability, efficacy, PK, and PD data obtained from the preceding cohorts (refer to Section 6, Dosage and Administration for additional details). After all the subjects in Part 1 are expected to have completed the Day10-14 visit, an unblinded data review will be conducted by the OC, Steering Committee (SC), Independent Data Monitoring Committee (IDMC), and sponsor to determine the dose range and doses for Part 2. A schematic diagram of the study design (Part 1) is provided in [Figure 1](#) below.

Figure 1: Schematic Overview of Part 1 of the Study

‡ Double-dummy design: Subjects in both parts will receive a single dose of IV JNJ-64179375 or JNJ-64179375 placebo and 10 to 14 days of apixaban or apixaban placebo PO BID, followed by unilateral venography and follow-up study visits through Week 18. Unique subjects will be enrolled in each part and within each part unique subjects will be enrolled in each cohort.

† Six cohorts of up to approximately 50 unique subjects per cohort (total of up to approximately 300 unique subjects) are planned but the number of cohorts and the size of each cohort may be adjusted based on the ongoing unblinded data review by the Operations Committee.

BID = twice daily; IV = intravenous; PO = by mouth

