3.1.1. Dose Escalation Decision Guidelines

OC will review data in an ongoing basis and make a dose escalation decision with intention to study at least 25 subjects at the current dose before escalating to the next higher dose. Dose escalation will be based on the totality of both efficacy and safety data coming from the current and previous cohorts.

Suggested Stopping criteria: meeting any of the following criteria in the highest dose studied could prohibit further dose escalation

- The lower bound of 1-sided 90% CI for major bleeding endpoint is greater than 2%, 3% or 4%.

The following thresholds for major bleeding, based on these rates, will be referenced and are suggested as a guideline when making dosing decisions. Bleeding that is high enough that it crosses one of the thresholds may require stopping dose escalation.

[Table 2](#) can also be used as a suggested threshold for escalating the dose based on the composite major VTE endpoint (proximal DVT, non-fatal PE or any death).

Table 2: Suggested Threshold to Stop Dose Escalation Based on Number of Subjects with Major Bleeding Events

Number of Events	Number of Subjects with Major Bleeding Events		
	Reference Rate: 2%	Reference Rate: 3%	Reference Rate: 4%
2	Up to 26 (7.7%)	Up to 17 (11.8%)	Up to 13 (15.4%)
3	Up to 55 (5.5%)	Up to 37 (8.1%)	Up to 28 (10.7%)
4	Up to 87 (4.6%)	Up to 58 (6.9%)	Up to 44 (9.1%)
5	Up to 122 (4.1%)	Up to 81 (6.2%)	Up to 61 (8.2%)
6	Up to 158 (3.8%)	Up to 105 (5.7%)	Up to 79 (7.6%)
7	Up to 195 (3.6%)	Up to 130 (5.4%)	Up to 98 (7.1%)
8	Up to 233 (3.4%)	Up to 156 (5.1%)	Up to 117 (6.8%)
9	Up to 272 (3.3%)	Up to 182 (4.9%)	Up to 137 (6.6%)
10		Up to 208 (4.8%)	Up to 156 (6.4%)
11		Up to 235 (4.7%)	Up to 177 (6.2%)
12		Up to 262 (4.6%)	Up to 197 (6.1%)

*Smallest number of events that result in the lower bound of the one-sided 90% confidence interval exceed thresholds.

- The lower bound of 1-sided 90% CI for the difference in any bleeding event rate between the JNJ-64179375 arm and the apixaban arm is greater than 0.

Table 3: Examples Where the Lower Bound of 1-sided 90% CI for the Between-Treatment Difference is Greater than 0

JNJ-64179375	Apixaban	Lower Bound
8/25 (32%)	1/10 (10%)	1%
5/25 (20%)	1/20 (5%)	2%
9/50 (18%)	3/40 (7.5%)	1%

- The lower bound of 1-sided 90% CI for the difference in the composite of major and clinically relevant nonmajor (CRNM) bleeding event rate between the JNJ-64179375 arm and the apixaban arm is greater than 0.

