Continual Reassessment Method (CRM), a model based approach commonly used in oncology dose escalation study to determine Maximum Tolerated Dose (MTD), will also be employed to predict event rates in next higher dose to guide the dose escalation process.

After all subjects are expected to have completed the Day 10-14 visit for Part 1, an unblinded data review is planned and the selection of the dose range and doses for Part 2 will be based on the evaluation of the totality of the data but with a focus on the any bleeding and total VTE endpoints.

The following sections describe details of the analysis and summary of Part 1 data.

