b) For the unblinded data review planned after all subjects are expected to have completed the Day 10-14 visit for Part 1, the following summary and analysis will be performed.

- Incidence of total VTE, major VTE with associated component events up to day 10-14 visit observation period will be summarized by treatment group for the modified ITT (mITT) analysis set. 90% confidence intervals for the odd ratio of each JNJ-64179375

dose over apixaban event rate with respect to Total VTE and Major VTE events will also be constructed.

- Dose response of JNJ-64179375 with respect to total VTE will be assessed using a two-stage generalized least squares approach model fitting methodology (Pinheiro et al, Stat in Med, 2013). That is, in the first stage, ANOVA-type model to the binary, total VTE data, based on the logistic regression model are fit using dose as factor. In the second stage, various candidate models (on logit scale) are fit using the estimates (from first stage) employing the Multiple Comparisons and Modeling (MCPMod) approach to the dose levels and associated variance-covariance matrix estimates from stage 1. The following candidate models will be considered: linear, emax, exponential, logistic and sigEmax. Dose-response effect are tested using a model-based multiple contrast test to select one (or several) model(s) from the significant shapes. The best fitting model to the data are picked using either the gAIC or aveAIC model selection criterion. The model with the smallest gAIC or aveAIC value is considered to fit the data best. Plots of the observed data and model fit including the 95% confidence intervals of the fitted lines will be presented using response rate on the y-axis and dose on the x-axis

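### The Part 1 dose-response model has no rule for a dose with no events; as written, such a dose gets essentially no weight, and a real trend can be missed

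*SAP*

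**What the plan says.** SAP 6.1.2, part b, describes a two-stage generalised least squares fit for any bleeding: "in the first stage, ANOVA-type model to the binary, Any bleeding data, based on the logistic regression model are fit using dose as factor". Stage 2 then applies the MCP-Mod "approach to the dose levels and associated variance-covariance matrix estimates from stage 1". SAP 5.2.3, part b, uses the same method for total VTE, again a model "based on the logistic regression model are fit using dose as factor". A multiple contrast test picks among the significant shapes, and gAIC or aveAIC chooses the best fit.

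No penalised, exact or Bayesian fit, continuity correction or zero-event rule is given. SAP 5.1.2 (Data Handling Rules) has a heading but no text. For the two-sample rate difference, SAP 6.1.2, part a, does guard against extreme proportions. It prefers the Miettinen-Nurminen method to Wald because the former "does not produce undesirable results in extreme cases (eg, when the proportions are near 0 or 1".

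Each cohort plans about 40 active subjects, though "the number of cohorts and the size of each cohort may be adjusted based on the ongoing unblinded data review" (SAP 1.2). Escalation proceeds "with intention to study at least 25 subjects at the current dose before escalating to the next higher dose" (SAP 3.1.1). Part 2 doses are chosen on the "totality of the data but with a focus on the any bleeding and total VTE endpoints" (SAP 3.1.1).

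**The concern.** With dose as a factor, stage 1 estimates one free logit per dose. If a dose has no events, the maximum-likelihood logit runs to minus infinity. Software stops at some large negative value with an enormous standard error, and stage 2 weights by the inverse variance, so the dose is effectively removed.

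The removal comes when the dose is most informative: no bleeding at the lowest dose, or no VTE at the highest. Dose response for these two endpoints is a Part 1 secondary objective, and both are the stated focus of Part 2 dose selection. Going from one event to none at the low dose should strengthen a bleeding trend. Under the written method it weakens the test. With no rule in the SAP, the remedy would have to be improvised at an unblinded review.

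**Working it through.** **The plan's own figures.** SAP 1.4 gives 67% (40 v 30 subjects) and 81% (80 v 40) for flagging 22.5% against 7.5% at 1-sided 10%. For 40 v 30 with pooled variance: pooled rate 11.25/70 = 0.161, null SE 0.0887, alternative SE 0.0817, and Φ[(0.15 − 1.2816 × 0.0887)/0.0817] = 67.2%. The same formula for 80 v 40 gives 81.3%. Both reproduce. Neither is in dispute, and neither concerns the dose-response model.

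**Inputs.** Doses of 0.3, 0.6 and 1.2 mg/kg and about 40 per dose (SAP 1.2). Rates from Table 7 of Protocol 11.2, which says "if the true underlying total VTE and any bleeding event rates are as specified in Table 7": any bleeding 5%, 6%, 8%; total VTE 15%, 10%, 6%. These are Part 2 planning rates, so using them for Part 1 is an assumption. At 80% evaluable venography (Protocol 11.2), 40 subjects give 32.

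**Weight of a zero-event dose.** For 0/40, one standard routine stops at logit −23.6 with SE about 12,600. With 4/40 at the other two doses, its share of the weight is about 10⁻⁹. A Firth fit with dose as the only factor equals adding 0.5 to events and to non-events. It gives logit ln(0.5/40.5) = −4.39, SE about 1.4 and a 5.8% share of the weight.

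**Effect on the linear contrast** (contrast built from the estimated covariance):
- 0, 2, 5 of 40, as written: only the upper two doses count. T = [ln(5/35) − ln(2/38)] / √(1/5 + 1/35 + 1/2 + 1/38) = 0.998/0.869 = **1.15**.
- 1, 2, 5 of 40, as written: weights 0.975, 1.900, 4.375; slope 1.81; T = **1.73**.
- 0, 2, 5 of 40, Firth stage 1: T = **1.74**, or 1.72 if the variance uses the unaugmented information.

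The SAP does not say how contrasts are derived. If they come from the estimated covariance, the zero dose drops out and, with three doses, every shape reduces to the same comparison of the other two. If they are fixed in advance for equal group sizes (linear: −0.617, −0.154, 0.772), the huge SE stays in the denominator and T for 0, 2, 5 collapses to about 0.002. Either way the zero dose does not inform the test.

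**How often.** P(at least one zero) = 1 − Π[1 − (1 − p)ⁿ].
- Any bleeding, n = 40: (1 − p)ⁿ = 0.129, 0.084, 0.036; result **23.0%**. At n = 80: 2.5%.
- Total VTE, n = 32: 0.006, 0.034, 0.138; result **17.2%**. At n = 64 (80 enrolled): 2.0%.
- Any bleeding at a common 15%, n = 40: 0.5%.

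**Signal rates.** Exact enumeration over event counts, single linear contrast, unadjusted 1-sided 10% (T > 1.28), Firth used only when a zero occurs:

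| | Given exactly one zero dose: as written / Firth | All datasets: as written / with the rule |
|---|---|---|
| Any bleeding, n = 40 | 14% / 25% | 14.9% / 18.2% |
| Total VTE, n = 32 | 25% / 61% | 33.2% / 39.4% |

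**False signals.** With flat true rates of 5% to 10% and 25 to 40 per dose, T exceeds 1.28 in 5.5% to 7.7% of datasets with the rule, against 1.9% to 7.1% as written. Both stay below the nominal 10%.

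**The case against.** The strongest reply is that no decision rests on this fit. Part 1 tests no hypothesis, Part 2 doses come from the totality of the data, and 0/40 is plain in the incidence table and the observed-data plot. The OC charter and the Data Presentation Specifications were not available and may cover it. That the fit is unpenalised is inferred from the SAP's silence. All of this stands and limits the severity. It does not repair the trend test or the curve, which the SAP specifies for that same review.

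Stronger readings are tempting, but the documents do not support them.

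- *The sponsor would carry forward a curve that is flat or points the wrong way.* Such fits do occur. Data of 0, 4, 4 of 40 give a flat 10%, and 4, 5, 0 of 32 give a line rising to 23.7% at the dose with no VTE. But the SAP selects only from significant shapes. In the expected direction these datasets give T = 0.00 and −0.36, so neither curve would be selected.
- *Half of trials are affected.* With 25 per dose the bleeding figure is 50%, but 25 is the intended minimum before escalating, not the planned size at the end of Part 1.
- *Every shape always gives the same statistic.* That needs contrasts built from the estimated covariance, which the SAP does not state.

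Two further points are fair. The signal rates above are for one unadjusted contrast, not the SAP's multiple contrast test, and the SAP states no level for that test. And the gain over all datasets is only about 3 percentage points for bleeding (18.2 − 14.9) and 6 for VTE (39.4 − 33.2).

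**Conclusion.** The point holds as a gap in the written method with a modest expected cost. A zero-event dose contributes essentially nothing to stage 2, and the consequence is mainly a missed dose-response signal, not a misleading curve carried into Part 2. It arises in roughly one trial in five at the planned cohort size, and in about 2% if doses are repeated to 80. If solicited bleeding brings the rate to about 15%, the bleeding figure is well below 1% and the point then mainly concerns VTE.

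These sizes assume Part 2 planning rates in Part 1, three doses, 80% evaluable venography and a single linear contrast at 1-sided 10%. The claim is about the Part 1 SAP text only. Cheap improvement, low to moderate severity.

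**What to change.** Add to SAP 5.2.3(b) and 6.1.2(b): *If any dose in the analysis has no events, stage 1 for that endpoint is fitted at all doses by Firth-penalised logistic regression; its estimates and covariance are passed to stage 2 and used to derive the contrasts.*

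This keeps the two-stage method and, for zero-event datasets, settles how contrasts are formed. Fitting the candidate curves directly by binomial likelihood also uses the zero dose. It replaces the two-stage method, however, so it suits a sensitivity analysis.

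The cost is one sentence and a standard software option. Stage 1 is unchanged when every dose has at least one event. In a zero-event dataset the other doses shrink slightly: 2/40 becomes 2.5/41 = 6.1% instead of 5.0%, and 0/40 enters as 0.5/41 = 1.2%. The estimator does switch with the data, but the trigger is written in advance and does not depend on the direction of the effect. Firth recovers only part of the information in the zero dose.

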6.2. Major (Key) Secondary Safety Endpoints

All individual components of the primary safety endpoint

- Major bleeding,
- Clinically relevant nonmajor bleeding,
- Minimal bleeding

Composite of major and clinically relevant nonmajor bleeding

6.3. Other Secondary Safety Endpoints

Any wound or joint complication in the operated leg

The following maps the location in eCRF of wound or joint complication in the operated leg

Wound or Joint Complications	eCRF Page # (s)	Comments
Wound or Joint Complications	Wound or Joint Complications	

Table 6 presents layout how Wound or Joint Complications will be summarized by treatment group for the safety analysis set(s).

Table 6: Wound or Joint Complications

Wound Complications for the operated leg/ surgical site (a)	Summary Type
Infection	Use the analogy of AE summary by SOC and Preferred term where (a) and (b) play the role of SOC and items underneath play the role of Preferred term
Poor Wound Healing	
Edema	
Erythema	
Other	
Joint Complications (b)	Provide in the summary, the number of subjects with any wound or joint complication in the operated leg
Infection	
Loosening	
Instability	
Periprosthetic fracture	
Abnormal joint pain	
Other	.

6.4. Adverse Events

The verbatim terms used in the CRF by investigators to identify adverse events will be coded using the Medical Dictionary for Regulatory Activities (MedDRA). Any AE occurring at or after the initial administration of study agent through the day of last dose to up to last contact date is considered to be treatment emergent. If the event occurs on the day of the initial administration of study agent, and either event time or time of administration are missing, then the event will be assumed to be treatment emergent. If the event date is recorded as partial or completely missing, then the event will be considered to be treatment emergent unless it is known to be prior to the first administration of study agent based on partial onset date or resolution date. All reported treatment-emergent adverse events will be included in the analysis. For each adverse event, the number and percentage of subjects who experience at least 1 occurrence of the given event will be summarized by treatment group. In addition, comparisons between treatment groups will be provided if appropriate.

Summary tables will be provided for:

- All AEs and TEAEs
- All Serious AEs (SAEs) and TESAEs
- AEs leading to discontinuation of study agent/termination of study participation
- TEAEs by severity
- TEAEs by relationship to study agent

In addition to the summary tables, listings will be provided for subjects who:

- Had SAEs
- Had AEs leading to discontinuation of study agent

Incidence of other treatment-emergent adverse events of special interest will be summarized.

As per protocol, adverse events of special interest include bleeding events, infusion reactions, hypersensitivity reactions, and wound or joint complications. All suspected symptomatic efficacy(thrombotic) events will also be captured as adverse events of special interest. Subjects with adverse events of special interest may be counted or listed using MedDRA SMQs (eg, hemorrhage excluding laboratory terms SMQ).

The following maps the location in eCRF of adverse events of special interest

Adverse events of special interest	eCRF Form names(s)	Comments
Specify AE special interest type	Adverse Events/Serious AEs	

Deaths will be displayed by actual treatment received. Frequencies for the following parameters will be included in the summary table:

- Number of subjects who died
- Cause of death
- Relationship to study agent (yes/no)

A listing of subjects who died will be provided.

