11.11. Committees

11.11.1. Operations Committee

During Part 1 of the study, an OC consisting of members of the academic leadership of the study, including the SC and IDMC chairpersons, and clinical and biostatistics representatives from the sponsor (not directly involved in study monitoring) will review ongoing unblinded safety and efficacy data. The OC will be responsible for:

- Reviewing ongoing safety and efficacy data by unblinded subject treatment assignments approximately every 1 to 3 weeks
- Determining the cohort sizes and number of cohorts for the up to approximately 300 unique subjects in Part 1
- Making dose-escalation decisions in Part 1, including but not limited to deciding whether to proceed with optional cohorts and at what dose(s)

• Reviewing the data for Part 1

The details of the OC function and composition, as well as dose-escalation decision guidelines will be described in the OC charter.

After all the subjects to be enrolled in Part 1 are expected to have completed the Day 10-14 visit, an unblinded review of available preliminary safety, tolerability, efficacy, PK, and PD data will be conducted to determine the dose range and number of dose groups (maximum of 4 for JNJ-64179375 and 1 for apixaban) for Part 2. This Part 1 data review will be conducted by the OC, SC, IDMC, and the sponsor.

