2.4.4. Safety Analysis Set

Safety analysis set includes all randomized subjects who received at least 1 dose (partial or complete) of active study drug

Safety Per Protocol analysis set includes all randomized subjects with no major protocol deviations who received the single complete infusion of JNJ-64179375 or at least 18 doses of oral apixaban or with a bleeding event centrally adjudicated by the Clinical Events Committee (CEC) within 2 days of the last dose of oral study drug

Safety Per Protocol analysis set details: Safety Per Protocol analysis set includes all randomized subjects, in the Up to Day 10-14 visit observation period with:

- No major protocol deviations (see section 4.5 for major protocol deviation)
→ this is expected to come from Data Management
- Subject received the single complete infusion of JNJ-64179375 or at least 18 doses of oral apixaban
→ that is, in the “Study Drug Administration” eCRF form for JNJ-64179375, “Was the Total administered?” should be equal to “Yes” or for apixaban, total # doses ≥ 18 .
- Subject bleeding event centrally adjudicated by the CEC within 2 days of the last dose of oral study drug
→ that is, CEC adjudicated bleeding event date \leq last oral (apixaban) dose date + 2 days

The 3 observation periods to be used in the bleeding event analyses include the following:

- Up to Day 10-14 visit (venography assessment)
- Up to the Week 5 visit
- Up to the Week 18 visit

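### If the SAP's adverse event and wound or joint tables are run for the Part 1 dose-selection review, the last-enrolled dose can look safer merely because it was observed for less time

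*SAP*

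**What the plan says.** SAP 6.4 counts as treatment emergent "Any AE occurring at or after the initial administration of study agent through the day of last dose to up to last contact date". It adds that "All reported treatment-emergent adverse events will be included in the analysis", and for each event "the number and percentage of subjects who experience at least 1 occurrence of the given event will be summarized by treatment group". SAP 6.3 summarizes wound or joint complications by treatment group on the safety set, modelled on the adverse event tables, with no observation period. That set has no follow-up requirement: "Safety analysis set includes all randomized subjects who received at least 1 dose (partial or complete) of active study drug".

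Observation periods exist for other data. SAP 2.4.4 lists Day 10-14, Week 5 and Week 18 under the words "The 3 observation periods to be used in the bleeding event analyses include the following", and SAP 2.4.3.2 lists Day 10-14 and Week 18 for efficacy. Total VTE (SAP 5.2.1), any bleeding (6.1.1) and other thrombotic events (5.4.2) are tied to Day 10-14. Laboratory results are shown by visit (6.5), and disposition is split at Day 10-14 (4.2).

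On timing, SAP 3.1.1 says: "After all subjects are expected to have completed the Day 10-14 visit for Part 1, an unblinded data review is planned". Protocol 11.11.1 gives its content: "an unblinded review of available preliminary safety, tolerability, efficacy, PK, and PD data will be conducted to determine the dose range". SAP 2.3 foresees a data cut-off while the study is still running.

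**The concern.** Cohorts are enrolled in sequence (0.3, 0.6 and 1.2 mg/kg, then optional cohorts), so calendar time, and with it observed follow-up, is tied to dose. A percentage of subjects with an event up to last contact rises with follow-up. At the review cut the first cohort has had the most time to accumulate events and the last cohort the least. Apixaban subjects, pooled over cohorts, fall in between. Neither section offers a common cut-off, a time-to-event summary or an exposure-adjusted rate to offset this.

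The safety and tolerability of each dose level is the Part 1 primary objective, and wound or joint complications against apixaban is a secondary one. At the review, a reader of these tables could take a difference in observation time for a difference between doses.

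**Working it through.** **The plan's own figure.** The documents give no operating figure for adverse events or wound and joint complications. The only one for Part 1 concerns any bleeding (SAP 1.4): 67% for 40 vs 30 subjects at 22.5% vs 7.5%. It reproduces with a pooled-variance normal approximation, one-sided 10%. The pooled rate is (9 + 2.25)/70 = 0.161, the null SE 0.0887 and the alternative SE 0.0817, so Φ((0.15 − 1.2816 × 0.0887)/0.0817) = 67.2%. For 80 vs 40 the result is 81.3% (stated 81%). These figures are untouched, because any bleeding has a fixed window.

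**Inputs from the documents.** Sequential cohorts of about 40 + 10 subjects (SAP 1.2). Maximum follow-up 14 + 112 = 126 days (SAP 1.2). Cut taken as 14 days after the last enrolment (from SAP 3.1.1).

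**Assumed, not in the documents.** Accrual of 3, 6 or 10 weeks per cohort. The same true risk at every dose, 5% or 10% by Day 14. Either a constant hazard, or 80% of the 126-day cumulative hazard in the first 14 days (front-loaded).

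**Step 1, follow-up.** F = min(126, cut − enrolment day). With three 6-week cohorts the cut is 3 × 42 + 14 = day 140.
- First cohort: F runs from 140 down to 98, capped at 126. One third sit at 126 and two thirds average 112, so the mean is 116.7 days.
- Last cohort: F runs from 56 down to 14, mean 35 days.

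**Step 2, expected crude percentage.** The mean over the cohort of 1 − exp(−H(F)). For 5% by Day 14, H(14) = −ln 0.95 = 0.0513. Constant hazard: H(F) = 0.0513 × F/14. Front-loaded: H(F) = 0.0513 + 0.25 × 0.0513 × (F − 14)/112. First vs last cohort, with the gap in points:

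| Cohorts × weeks | Mean days | Constant, 5% | Front-loaded, 5% | Constant, 10% | Front-loaded, 10% |
|---|---|---|---|---|---|
| 3 × 3 | 66.5 vs 24.5 | 21.6 vs 8.6 (13.0) | 5.6 vs 5.1 (0.5) | 39.3 vs 16.7 (22.6) | 11.1 vs 10.2 (0.9) |
| 3 × 6 | 117 vs 35 | 34.7 vs 11.9 (22.8) | 6.1 vs 5.2 (0.9) | 58.3 vs 22.8 (35.5) | 12.1 vs 10.4 (1.7) |
| 3 × 10 | 126 vs 49 | 37.0 vs 16.2 (20.8) | 6.2 vs 5.4 (0.8) | 61.3 vs 30.0 (31.3) | 12.3 vs 10.7 (1.6) |
| 6 × 3 | 125 vs 24.5 | 36.7 vs 8.6 (28.1) | 6.2 vs 5.1 (1.1) | 60.9 vs 16.7 (44.2) | 12.3 vs 10.2 (2.1) |
| 6 × 6 | 126 vs 35 | 37.0 vs 11.9 (25.1) | 6.2 vs 5.2 (1.0) | 61.3 vs 22.8 (38.5) | 12.3 vs 10.4 (1.9) |

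**Step 3, against pooled apixaban.** With equal apixaban numbers per cohort, three 6-week cohorts and 5% by Day 14, pooled apixaban shows (34.7 + 24.5 + 11.9)/3 = 23.7% against 11.9% for the last dose under a constant hazard. Front-loaded, it shows (6.1 + 5.7 + 5.2)/3 = 5.7% against 5.2%.

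**Step 4, a second event-time model.** Three 8-week cohorts give a cut at week 26 and mean follow-up of 18, 14 and 6 weeks. The share of 18-week events seen in the last cohort relative to the first is:
- events uniform over 18 weeks: 6/18 = 0.33
- half in the first 2 weeks: 0.5 + 0.5 × 4/16 = 0.625
- 80% in the first 2 weeks: 0.8 + 0.2 × 4/16 = 0.85

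Pooled apixaban has mean follow-up 38/3 = 12.7 weeks, and the corresponding ratios are 0.47, 0.75 and 0.91.

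**Step 5, common window.** Counting to Day 14 for everyone returns 5% vs 5%, or 10% vs 10%, in every scenario.

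**The case against.** The link from these tables to the dose decision is inferred. Dose selection focuses on any bleeding and total VTE, both with a fixed primary window, and the review analyses in SAP 5.2.3(b) and 6.1.2(b) name no adverse event or wound table. The SAP's end-of-Part-1 topline report carries no date, and several summaries run to Week 18. The Operations Committee charter and the table specifications are separate documents, not available here. No hypothesis is tested, and the committee sees unblinded data every 1 to 3 weeks, so it would know the cohort timing. All of this stands and limits the scope. It does not remove the imbalance from tables run at the early cut, and Protocol 11.11.1 does put available safety and tolerability data before that review.

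Protocol 11.9 defines treatment-emergent events mainly by onset in the treatment phase, which Protocol 3.2 puts at up to 14 days. The protocol therefore already implies a nearly common window, and SAP 6.4 departs from it. This stands, and it points to part of the fix.

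A half-life of about 25 days suggests that much exposure falls after Day 14: 2^(−14/25) = 68% under simple exponential decay. The Phase 1 table shows a distribution phase (at 0.3 mg/kg, dose/Cmax = 300/6.86 = 43.7 mL/kg against a Vz of 78.8), so 68% is nearer an upper bound. Late events are plausible but not shown.

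Three stronger readings are tempting and not supported:
- A reader might infer that the last dose will look safer only because of follow-up. A true difference may also exist.
- A reader might infer that the bias always hides a dose-related rise. Optional cohorts may use any dose from 0.1 to 1.8 mg/kg or repeat one (Protocol 6), so the last cohort need not be the highest.
- A reader might infer that the distortion is always material. The 0.91 ratio and the 5.6% vs 5.1% case show that it can be small.

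**Conclusion.** The concern holds for the adverse event and wound or joint tables, on the condition that they are produced before all Part 1 subjects reach Week 18. At the review cut the crude percentages compare doses over unequal follow-up, always in favour of the last-enrolled cohort relative to earlier ones and to pooled apixaban. A comparison with apixaban subjects of the same cohort is not biased in this way. The effect on the apparent dose trend depends on the last cohort: it hides a rise if that cohort has the highest dose, exaggerates one if it has a lower dose, and is diluted if it repeats a dose.

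Under the assumed accrual and event timing, the gap runs from 0.5 points to more than 30 (44.2 at the extreme of the grid). The large values need a roughly constant hazard over 18 weeks, which the documents do not establish. The main basis for choosing Part 2 doses is not affected. The change is worth making before the review.

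**What to change.** In SAP 6.3 and 6.4, for any table produced before all Part 1 subjects reach Week 18:
- Count treatment-emergent and serious adverse events, deaths, and wound or joint complications up to the Day 10-14 visit for all treated subjects.
- Show later events separately, as Kaplan-Meier incidence or events per subject-week, and report follow-up time by dose. Keep the rate to the period after Day 14: over the whole follow-up, front-loaded events would reverse the bias (three 6-week cohorts, 5% by Day 14: roughly 6.1/116.7 = 0.05 against 5.2/35 = 0.15 per 100 subject-days).
- Define any Week 5 table by calendar eligibility (randomized at least 5 weeks before the cut), so that subjects who died or withdrew stay in the denominator.

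Keep the window to last contact for the final tables. Reconcile the treatment-emergent definition in SAP 6.4 with Protocol 11.9.

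The cost is SAP wording, a date filter on tables already planned, and a few more outputs at the review.
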